5.2. Participant Dispositions

Number of participants screened for the study will be provided. Summary of study disposition will be provided by study intervention for the following:

- Number of participants enrolled/randomized
- Number of participants treated
- Number of participants completed the study
- Number of participants discontinued the study
- Reasons for discontinuation

CONFIDENTIAL

Draft Statistical Analysis Plan v2.0

XEN-45 Gel Stent

5.3. Primary Endpoint Analysis

It is essential to note that when IOP measure at a visit is referred, it usually stands for the mean of 3 IOP readings for a patient performed within 24 hours at a given visit.

5.3.1. Definition of Primary Endpoint

The primary effectiveness endpoint is the proportion of responders meeting all criteria below:

- Achieving $\geq 20\%$ mean IOP reduction from baseline at Month 12
- No increase in number of topical IOP-lowering medications at Month 12 compared to the baseline
- No clinical hypotony
- No loss of vision to count fingers or worse
- No secondary glaucoma surgical intervention.

The IOP will be assessed at all study visits by standard Goldmann Applanation Tonometry. For each IOP assessment, two consecutive measurements will be taken for each eye. If these 2 measurements differ by > 1 mm Hg, a third measurement will be performed for the given eye. The IOP value for a given eye will be the average of all measurements, which will be obtained from the eCRF, and the percent change from baseline at Month 12 will be computed as

$$\text{Percent change} = \frac{\text{Month 12 IOP} - \text{Baseline IOP}}{\text{Baseline IOP}} \times 100$$

The subject having the computed value of ≤ -20 will be considered achieving $\geq 20\%$ mean IOP reduction from baseline at Month 12.

The usage of topical IOP-lowering medication will be collected in the concomitant medication page. The IOP-lowering medication that were started before the Month 12 visit and stopped on or after the Month 12 visit or recorded as ongoing will be considered as the medication taken at Month 12. The partial start and stop dates of the medication will be imputed based on missing dates imputation rules specified in Appendix 3.

The clinical hypotony is defined as vision reduction (2 lines or more) related to macular changes consistent with hypotony maculopathy (macular folds), optic disc edema, and/or serous choroidal detachments because of low IOP. The following steps provide the identification of a patient with clinical hypotony. A patient at any time point with the following conditions:

- 1- filter any eyes with IOP of 6 mmHg or less, from this list...
- 2- Filter any eyes with VA reduction 2 lines or more compare to baseline, from the eyes left (and this is where it becomes more clinical and difficult, but the n should not be too high at this point)...
- 3- Filter any eyes that reported on the "OPHTHALMOSCOPY CRF" abnormal macula or periphery; AND any eyes that reported any of these AE:
 - Anterior chamber shallow with peripheral irido-corneal touch
 - Anterior chamber flat with irido-corneal touch

CONFIDENTIAL

Draft Statistical Analysis Plan v2.0

XEN-45 Gel Stent

- BCVA loss of ≥ 2 lines (≥ 10 ETDRS letters)
 - ≤ 30 days
 - > 30 days
 - At 12 months (persistent loss)
- Choroidal effusion (extending posterior to equator, without blood)
- Choroidal effusion (obscuring disc or macula, without blood)
- Choroidal effusion (with choroids touching in the center of the eye, without blood)
- Choroidal effusion (extending posterior to equator, with blood)
- Choroidal effusion (obscuring disc or macula, with blood)
- Choroidal effusion (with choroids touching in the center of the eye, with blood)
- Choroidal effusion and/or hemorrhage occurring > 30 days (persistent)
- Hypotony maculopathy
- Macular edema

The Best Corrected Visual Acuity (BCVA) should be performed using a Snellen Chart with glasses at all study visits. For participants with vision loss that Snellen Chart cannot be used, the vision acuity will be collected as Count Fingers, Hand Movement, Light Perception, or No Light Perception. Patients with vision loss to count fingers will be counted as not meeting the criteria.

The secondary glaucoma surgical intervention will be recorded in the glaucoma surgery eCRF page.

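### The steps that identify clinical hypotony do not implement the SAP's own definition, so primary responder status may be misclassified in either direction

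*SAP*

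**What the plan says.** SAP 5.3.1 lists "No clinical hypotony" among the five responder criteria. It defines the condition as a drop in vision of at least two lines that is tied to "macular changes consistent with hypotony maculopathy (macular folds), optic disc edema, and/or serous choroidal detachments because of low IOP". Protocol 7.2 gives the same definition.

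The SAP then turns this into a sequence of filters. The lead-in reads "A patient at any time point with the following conditions", with no visit or window named. The filters are:

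1. Pressure: only eyes with an IOP at or below 6 mm Hg are kept.
2. Vision: the instruction here is "Filter any eyes with VA reduction 2 lines or more compare to baseline, from the eyes left".
3. Finding: this step needs an ophthalmoscopy form reporting "abnormal macula or periphery; AND any eyes that reported any of these AE".

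The AE list attached to step 3 holds shallow and flat anterior chamber, "BCVA loss of ≥ 2 lines (≥ 10 ETDRS letters", choroidal effusions without and with blood, hypotony maculopathy and macular edema. The optic disc appears there only as something an effusion may hide, as in "Choroidal effusion (obscuring disc or macula, without blood".

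SAP 5.4.2 also makes absence of clinical hypotony a criterion for complete and for qualified success.

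**The concern.** The definition and the steps sit next to each other and disagree. One of the three qualifying findings has no entry in the steps. The connective in step 3 can be programmed in two ways, and neither reproduces the definition. The two causal links in the definition (vision loss related to the finding, finding due to low IOP) have no counterpart: there is no same-visit rule, time window, comparison of the ophthalmoscopy finding with baseline, or case review.

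Two programmers working from this text could therefore derive different hypotony flags, and so different primary endpoints, from the same data. A flagged eye that meets every other criterion becomes a failure, and a missed eye stays a responder. The trial is open-label and small, so the rule should be settled before anyone sees which eyes it affects.

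**Working it through.** **Definition against steps.** Each row is an eye that has had IOP of 6 mm Hg or less and a two-line loss, with the filters applied per eye across visits. These are constructed cases, not trial data.

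| Eye | Definition | Step 3, both sources | Step 3, either source |
|---|---|---|---|
| Macular folds at ophthalmoscopy, vision-loss AE reported | yes | yes | yes |
| Macular folds at ophthalmoscopy, no listed AE recorded | yes | no | yes |
| Disc edema only, vision-loss AE reported | yes | no | yes, but only through the vision-loss AE |
| Disc edema only, no listed AE recorded | yes | no | no |
| Low IOP on Day 1, cataract-related loss at Month 9, vision-loss AE, normal fundus | no | no | yes |
| Same, with an old macular abnormality on the form | no | yes | yes |
| Shallow-chamber AE, no macular, disc or choroidal finding | no | no | yes |

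The definition holds if any one finding is present. The both-sources reading is too strict in rows 2 to 4 and too loose in row 6. The either-source reading is too loose in rows 5 to 7 and still misses row 4. Rows 5 and 6 depend on the filters running across visits; if all conditions must hold at one time point, they drop out.

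**Arm sizes.** SAP Section 3 gives 68 and 34 completers, a 70% trabeculectomy rate and a 24-point margin. Assuming 70% in both arms, with one-sided 5% and 80% power:

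n(trabeculectomy) = (1.645 + 0.842)² × 0.21 × (1 + 1/2) / 0.24² = 33.8, so 34; XEN 68; total 102; 102 / 0.9 = 113.3, so 114.

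The plan's figures reproduce. They contain nothing on hypotony, so no corrected hypotony figure can be computed.

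**What one eye is worth (illustration).** 1/68 = 1.47 points in XEN; 1/34 = 2.94 points in trabeculectomy.

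SAP 5.3.2 uses a normal-approximation 95% interval, and Section 2 sets the limit at -24%:

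lower limit = d − 1.96 × √[pX(1 − pX)/68 + pT(1 − pT)/34], with d = pX − pT.

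At 70% in both arms: √(0.21/68 + 0.21/34) = 0.0963, and 1.96 × 0.0963 = 0.189, so the lower limit is -18.9%.

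| Change from 70% in each arm | d (points) | Lower 95% limit |
|---|---|---|
| 1 XEN eye becomes a failure | -1.5 | -20.4% |
| 2 XEN eyes | -2.9 | -22.0% |
| 3 XEN eyes | -4.4 | -23.5% |
| 4 XEN eyes | -5.9 | -25.0% |
| 1 trabeculectomy eye becomes a failure | +2.9 | -16.2% |
| 2 trabeculectomy eyes | +5.9 | -13.6% |
| 3 trabeculectomy eyes | +8.8 | -10.8% |
| 2 trabeculectomy eyes wrongly kept as responders | -5.9 | -23.9% |

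Largest deficit that passes at pT = 0.70: with d = -0.0488, pX = 0.6512 and the standard error is 0.0976, so the limit is -0.0488 − 0.1912 = -0.240. That is about 4.9 points.

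With whole eyes near the margin (assumed counts), against 24/34 trabeculectomy responders, 45/68 XEN gives -23.4% and passes, while 44/68 gives -24.95% and fails. If one trabeculectomy eye is reclassified as a failure, 44/68 against 23/34 gives -22.3% and passes.

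**The case against.** Most of the defence concerns how far the text can be pushed, and much of it stands.

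- *Both sources are required.* A reader might infer this from the capitalised AND, but the phrase can equally mean that eyes with a listed AE are added. The text is ambiguous, not plainly an intersection.
- *Any eye with a finding in only one source is missed.* This goes too far. A two-line vision loss is itself a listed AE, and Protocol 10.1.2.1.2 says listed events should be reported. An eye that passes step 2 should normally have a qualifying AE, so folds seen only at ophthalmoscopy would usually still be captured. What remains under the both-sources reading is disc edema without a macular or peripheral abnormality, and incomplete AE recording.
- *Findings from different visits may be combined.* The SAP does not say so; its opening words can mean that all conditions hold at one time point. The timing is unspecified rather than wrongly specified. The separate low-IOP safety endpoint does tie its assessment to the low-IOP visits, which shows that the authors could have stated a link here.
- *Old macular disease will be flagged.* Exclusion criterion 13 removes active retinopathy, geographic atrophy and other confounding disease, so the pool is small. Pre-existing conditions are not AEs under the protocol unless they recur or worsen. The route that remains is the vision-loss AE.
- *The size.* The one-eye shifts belong to any small trial. At 70% in both arms, three XEN eyes can be lost and the trial still passes. Errors in the two arms partly cancel.
- *The hypotony safety summary is distorted as well.* SAP 5.6.3.1 gives the clinical definition without citing the steps, so this is not established.

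None of this supplies the missing disc-edema entry, settles the AND, or provides a timing and baseline rule.

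**Conclusion.** The steps contradict the definition they are meant to apply, and they feed a component of the primary endpoint. The omission of optic disc edema is certain from the text. The AND and the timing are ambiguous, and neither reading of the AND reproduces the definition.

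The supported conclusion is that clinical hypotony status may be misclassified in either direction. A reader might infer that eyes *are* misclassified, or that the error favours one arm. The documents support neither: they give no hypotony rate overall or by arm.

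The effect is 1.5 points per XEN eye or 2.9 points per trabeculectomy eye, and only for eyes that meet every other responder criterion. Against a tolerated observed deficit of 4.8 to 4.9 points, one eye matters near the margin and several are needed elsewhere. These figures assume 68 and 34 evaluable eyes, a 70% trabeculectomy rate and the unpooled normal-approximation interval. The point should be corrected before lock; it does not by itself undermine the trial.

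**What to change.** Rewrite step 3 to follow the definition:

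- Require at least one of macular changes consistent with hypotony maculopathy, optic disc edema or serous choroidal detachment, new since baseline, from ophthalmoscopy **or** a matching AE term. State the OR explicitly.
- Remove the vision-loss AE, which repeats step 2. Remove, or justify in the SAP, the listed AEs outside the definition: the anterior chamber events and the effusions with blood. A bare switch to OR with the present list would let these qualify alone.
- Require IOP of 6 mm Hg or less, the two-line loss and the finding at the same visit or within a stated number of days. A rule based on adjacent visits is too loose: Month 9 covers weeks 33 to 47 and Month 12 weeks 48 to 60, so two adjacent visits can be months apart.
- List the eyes that pass steps 1 and 2 and have them reviewed before lock, blind to treatment arm, for whether the loss is related to the finding and the finding is due to low IOP. Filters alone cannot decide this.

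The case report form is not among the documents, so whether it has an optic disc field is unknown. If it has none, use AE and free-text records and say so.

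The cost is a SAP revision, a little more programming and a short review of what should be few eyes.

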5.4. Secondary Endpoints Analysis

The analysis will be performed for the study eye using ITT population for efficacy and PRO.

5.4.1. Key/Confirmatory secondary endpoints

As there is no key secondary endpoint that is selected for label update and multiple testing adjustment, this section is not applicable.

5.4.2. Secondary endpoints

All secondary endpoints will be analyzed using ITT population for efficacy and PROs.

Effectiveness:

CONFIDENTIAL

Draft Statistical Analysis Plan v2.0

XEN-45 Gel Stent

- Mean and changes in mean IOP from preoperative baseline over time
- Number of topical IOP-lowering medications from preoperative baseline over time
- Mean and changes in mean IOP and number of topical IOP-lowering medications from preoperative baseline over time in eyes with medicated baseline IOP ≤ 18 mm Hg
- Change in mean IOP from medicated baseline at Month 12
- Change in mean number of topical IOP-lowering medications from medicated baseline, at Month 12
- Proportion of participants with IOP value of ≤ 18 mmHg at Month 12
- Proportion of participants with IOP value of ≤ 17 mmHg at Month 12
- Proportion of participants with IOP value of ≤ 16 mmHg at Month 12
- Proportion of participants with IOP value of ≤ 15 mmHg at Month 12
- Proportion of participants with IOP value of ≤ 14 mmHg at Month 12
- Proportion of participants with IOP value of ≤ 13 mmHg at Month 12
- Proportion of participants with IOP value of ≤ 12 mmHg at Month 12
- Proportion of participants achieving $\geq 25\%$ IOP reduction from baseline at Month 12
- Proportion of participants achieving $\geq 30\%$ IOP reduction from baseline at Month 12
- Proportion of participants achieving $\geq 35\%$ IOP reduction from baseline at Month 12
- Proportion of participants achieving $\geq 40\%$ IOP reduction from baseline at Month 12
- Proportion of participants achieving $\geq 45\%$ IOP reduction from baseline at Month 12
- Proportion of participants achieving $\geq 50\%$ IOP reduction from baseline at Month 12
- Proportion of participants meeting all following criteria:
 - $\geq 20\%$ IOP reductions at Month 12
 - IOP value of ≤ 18 mmHg at Month 12
 - Same or lower in number of topical IOP-lowering medications at Month 12 compared to the baseline
- Proportion of participants meeting all following criteria:
 - $\geq 20\%$ IOP reductions at Month 12
 - IOP value of ≤ 17 mmHg at Month 12
 - Same or lower in number of topical IOP-lowering medications at Month 12 compared to the baseline
- Proportion of participants meeting all following criteria:
 - $\geq 20\%$ IOP reductions at Month 12
 - IOP value of ≤ 16 mmHg at Month 12
 - Same or lower in number of topical IOP-lowering medications at Month 12 compared to the baseline
- Proportion of participants meeting all following criteria:
 - $\geq 20\%$ IOP reductions at Month 12
 - IOP value of ≤ 15 mmHg at Month 12
 - Same or lower in number of topical IOP-lowering medications at Month 12 compared to the baseline
- Proportion of participants meeting all following criteria:

CONFIDENTIAL

Draft Statistical Analysis Plan v2.0

XEN-45 Gel Stent

- $\geq 20\%$ IOP reductions at Month 12
- IOP value of ≤ 14 mmHg at Month 12
- Same or lower in number of topical IOP-lowering medications at Month 12 compared to the baseline
- Proportion of participants meeting all following criteria:
 - $\geq 20\%$ IOP reductions at Month 12
 - IOP value of ≤ 13 mmHg at Month 12
 - Same or lower in number of topical IOP-lowering medications at Month 12 compared to the baseline
- Proportion of participants meeting all following criteria:
 - $\geq 20\%$ IOP reductions at Month 12
 - IOP value of ≤ 12 mmHg at Month 12
 - Same or lower in number of topical IOP-lowering medications at Month 12 compared to the baseline
- Needling rates, number of needlings per eye, outcomes post needling, including mean IOP and number of medications measured by proportion of eyes achieving $>20\%$ reduction at 12 months on same or fewer topical IOP-lowering medications, and number of patients not using any topical IOP-lowering medications, antifibrotic use during needling

Complete and qualified success:

- Proportion of participants with complete success at Month 12 which is defined as meeting all following criteria in the study eye
 - IOP ≤ 18 mmHg at Month 12
 - $\geq 20\%$ reduction in IOP from medicated baseline, which is the IOP value at Baseline Qualifying Visit, at Month 12
 - No topical medications at Baseline Qualifying Visit
 - No clinical hypotony

The topical medication includes any topical ophthalmic medication used on the study eye regardless of the indication and dosage.

This endpoint will be analyzed among the participants without topical medication at Baseline Qualifying Visit.

- Proportion of participants with qualified success at Month 12 which is defined as meeting all following criteria in the study eye
 - IOP ≤ 18 mmHg at Month 12
 - $\geq 20\%$ reduction in IOP from medicated baseline, which is the IOP value at Baseline Qualifying Visit, at Month 12
 - Taking topical medications at Baseline Qualifying Visit
 - No clinical hypotony

CONFIDENTIAL

Draft Statistical Analysis Plan v2.0

XEN-45 Gel Stent

The topical medication includes any topical ophthalmic medication used on the study eye regardless of the indication and dosage.

This endpoint will be analyzed among the participants with topical medication at Baseline Qualifying Visit.

- Proportion of participants with IOP value of ≤ 18 mmHg at Month 12 in medication-free eye
- Proportion of participants with IOP value of ≤ 17 mmHg at Month 12 in medication-free eye
- Proportion of participants with IOP value of ≤ 16 mmHg at Month 12 in medication-free eye
- Proportion of participants with IOP value of ≤ 15 mmHg at Month 12 in medication-free eye
- Proportion of participants with IOP value of ≤ 14 mmHg at Month 12 in medication-free eye
- Proportion of participants with IOP value of ≤ 13 mmHg at Month 12 in medication-free eye
- Proportion of participants with IOP value of ≤ 12 mmHg at Month 12 in medication-free eye

- Proportion of eyes achieving specific percentage IOP lower targets from baseline (≥ 25 -50% in 5% increments) with medication-free eyes

Note: medication-free eye at Month 12 is defined as no IOP-lowering medication was used to the study eye at Month 12.

Intraoperative adjunctive antifibrotic therapy administered:

- Compound/product, mode of administration, dose and concentration, timing of adjunctive agent (surgery day and pre- and postsurgical procedure/implantation)

Note: The data will be presented only if they are collected on CRF.

Visual parameters recovery post surgery:

- Mean and mean change in best corrected visual acuity (BCVA) with current glasses (preoperative and postoperative Day 1, Weeks 1 and 2, and Months 1, 3, 6, 9, and 12)
- Mean and mean change in manifest refraction (baseline and postoperative Months 1, 3, 6, and 12)
- Mean and mean change in surgically induced astigmatism (autorefractor reading [preoperative and postoperative Months 1, 6, and 12] and, at selected sites, topography [preoperative and postoperative Week 1 and Months 1 and 12])
- Mean and mean change in optical biometry (anterior chamber depth and keratometric values [preoperative and postoperative Day 1 and Week 2]) at selected sites.

CONFIDENTIAL

Draft Statistical Analysis Plan v2.0

XEN-45 Gel Stent

Other:

- Bleb photography (anterior segment optical coherence tomography [AS-OCT] and slit lamp photography at selected sites).

Safety:

- Clinical hypotony defined as vision reduction (2 lines or more) related to macular changes consistent with hypotony maculopathy (macular folds), optic disc edema, and/or serous choroidal detachments because of low IOP
- Eyes with IOP 6 mm Hg or less at any time point and relevant clinical assessment (vision reduction [2 lines or more] related to macular changes consistent with hypotony maculopathy [macular folds], optic disc edema, anterior chamber status, and/or serous choroidal detachments because of low IOP) of these eyes at those time points
- Adverse events (AEs) including specific intraoperative and postoperative events of interest
- BCVA, pachymetry, visual field
- AE including serious AEs (SAEs)
- Adverse device effects (ADEs) including serious ADEs (SADEs)

Patient-reported Outcomes:

- Patient-reported Outcomes (PRO)

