### 8.3.2 Inclusion Criteria

To be eligible for study entry subjects must satisfy all of the following criteria in the study eye (only 1 eye will be allowed in the study):

1. Male or female subjects ages  $\geq 18$  years
2. Able to provide signed written informed consent
3. Glaucoma in which the IOP is not controlled on current topical IOP-lowering glaucoma medication
4. Best-corrected baseline Snellen visual acuity of 20/100 or better
5. Visual field mean deviation no worse than -18.0 dB (with no dense paracentral scotomas, eg,  $>18$  dB total deviation on 1 or more of the 4 paracentral points)
6. Medicated IOP  $\geq 15$  mm Hg and  $\leq 44$  mm Hg on at least 1 topical IOP-lowering medication
7. Subjects not anticipated to require any other ocular surgery (eg, cataract surgery) in either eye up to 3 months from the time of inclusion
8. Area of healthy, free, and mobile conjunctiva in the target area, ie, superior bulbar conjunctiva
9. Visible trabecular meshwork with Shaffer angle grade  $\geq 2$  in the target area or, in eyes with prior failed angle surgery, an open angle in the target area
10. Preoperative laser trabeculoplasty is allowed 3 or more months prior to randomization
11. Failed ab-interno canal or suprachoroidal MIGS procedures (such as i-Stent®, gonioscopy-assisted transluminal trabeculotomy [GATT], ab-interno canaloplasty [ABiC™], Kahook Dual Blade goniotomy, etc) are allowed 3 or more months before enrollment, with the exception of CyPass® Micro-Stents, which are not allowed. Ab-interno ablative procedures (such as endoscopic cyclophotocoagulation [ECP]) are also allowed 3 or more months before enrollment.

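### The seven combined secondary responder endpoints omit the primary endpoint's clinical-hypotony condition, so an eye that fails the primary for hypotony can pass all seven

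*SAP*

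**What the plan says.** SAP 5.4.2 defines three families of Month 12 responder endpoints under effectiveness:

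- seven plain pressure targets, 18 down to 12 mm Hg, the last being "Proportion of participants with IOP value of ≤ 12 mmHg at Month 12";
- six percentage reductions, 25% to 50% in steps of five;
- seven combined endpoints, each requiring a fall of at least 20%, one of the seven pressure targets, and "Same or lower in number of topical IOP-lowering medications at Month 12 compared to the baseline".

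None of these has a lower pressure limit or a hypotony condition. Protocol 7.2 and SAP 1.1.3 state the same families without one, and nothing in SAP 5.1 or 5.4.2.1 adds it. The medication-free versions, such as "Proportion of participants with IOP value of ≤ 12 mmHg at Month 12 in medication-free eye", are built the same way.

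The primary endpoint (SAP 5.3.1) does list "No clinical hypotony" as a criterion, and so do complete and qualified success in SAP 5.4.2. SAP 5.3.1 derives the flag in sequence, at any time point. It begins with "filter any eyes with IOP of 6 mmHg or less, from this list", then requires a loss of at least two lines of acuity, then an abnormal macula or periphery on ophthalmoscopy together with a listed adverse event.

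Low pressure is also reported under safety: "Eyes with IOP 6 mm Hg or less at any time point and relevant clinical assessment".

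**The concern.** The combined endpoints look like the primary endpoint with a pressure target added, so a reader will expect every combined responder to be a primary responder too. That does not follow. An eye can be a primary failure because it over-drained and lost vision, yet satisfy every combined endpoint because its pressure is low. The complication itself produces the success.

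At stake is how the secondary between-arm differences are read. SAP 5.4.2.1 excepts the effectiveness endpoints from purely descriptive reporting and gives categorical endpoints a 95% confidence interval for the treatment difference. (Its lead-in sentence names only complete and qualified success, so the scope is not fully clear.) If the operations differ in clinical hypotony, the arm with more of it gains responders, and the combined endpoints can diverge from the primary for a reason that is harm rather than pressure control.

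**Working it through.** The plan states no figure on this point, so there is nothing to reproduce. The check compares the definitions and then sizes one misclassified eye.

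**1. Definitions side by side**

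| Condition | Primary (SAP 5.3.1) | Complete / qualified success (SAP 5.4.2) | Seven combined (SAP 5.4.2) |
|---|---|---|---|
| Fall of at least 20% | yes | yes | yes |
| Pressure target | none | 18 mm Hg | 18 to 12 mm Hg |
| No added IOP-lowering drops | yes | defined by medication use | yes |
| No clinical hypotony | yes | yes | **absent** |

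**2. When an eye passes all seven**

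With no added medication, an eye passes all seven if Month 12 IOP ≤ 12 and (baseline − Month 12 IOP) / baseline ≥ 0.20, that is, Month 12 IOP ≤ 0.80 × baseline.

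- Baseline 15 mm Hg (the lowest medicated pressure allowed by Protocol 8.3.2): 0.80 × 15 = 12. From a baseline of 15 or more, any Month 12 pressure of 12 or less passes all seven.
- 15 to 6 mm Hg: (15 − 6)/15 = 60%. Passes 7 of 7.
- 10 to 6 mm Hg: (10 − 6)/10 = 40%. Passes 7 of 7. This case is included because SAP 5.1 generally takes baseline from Preoperative Visit 1, for which no entry minimum is stated.
- 15 to 12 mm Hg: (15 − 12)/15 = 20%. Passes 7 of 7.

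The combined set therefore does not separate an eye at 12 mm Hg from one at 6 mm Hg with clinical hypotony. With the condition added, a flagged eye passes 0 of 7.

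**3. Weight of one eye**

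SAP section 3 plans 68 XEN and 34 trabeculectomy completers.

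- XEN: 1/68 = 1.5 points.
- Trabeculectomy: 1/34 = 2.9 points.

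**4. Shift in the between-arm difference**

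Let h be the proportion of an arm that is flagged and would otherwise count as a responder. Adding the condition changes XEN minus trabeculectomy by h(trabeculectomy) − h(XEN). The documents give no rates, so these are assumptions:

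| XEN | Trabeculectomy | Shift (points) |
|---|---|---|
| 5% | 5% | 0 |
| 0% | 3% | +3 |
| 2% | 5% | +3 |
| 2% | 10% | +8 |
| 5% | 15% | +10 |

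If XEN had the higher rate, the sign would reverse.

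**The case against.** The strongest reply is that low pressure is not hidden. The endpoints meant to define clinical success carry the condition, and clinical hypotony and eyes at 6 mm Hg or less are tabulated under safety. There is no key secondary endpoint and no multiplicity scheme (SAP 5.4.1, 5.4.3). The SAP follows the protocol's own definitions, and the cut-offs within a family are nested, so this is one choice repeated rather than many errors. All of that is true and limits the weight. It does not answer the point about the combined set, because a separate safety table does not correct a responder rate.

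Three stronger readings are tempting, and the documents do not support them.

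- **Every responder endpoint is wrong.** The 7 plain targets and 6 percentage reductions, with their 13 medication-free counterparts, share the omission. But they describe the pressure distribution, which is a legitimate use, and turning them into safety composites is a trade-off rather than a correction.
- **Any very low eye with maculopathy fails the primary.** The flag also needs a two-line loss and the listed findings. An eye at 3 mm Hg without that loss can be a primary responder, so the conflict is confined to eyes that pass every step.
- **The bias must favour trabeculectomy.** Protocol 6.1 names excessive drainage and clinical hypotony among trabeculectomy complications, and 6.2.2 reports fewer complications with XEN in general. But Protocol 8.2.2 lists hypotony as a XEN risk and omits it from its own trabeculectomy risk list. The direction is a plausible expectation, not a given.

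**Conclusion.** The point holds for the seven combined endpoints. They repeat the primary's 20% fall and medication rule, add a pressure target and drop the hypotony condition that the plan applies to its other composite success definitions. An eye flagged for clinical hypotony, with low Month 12 pressure and no added drops, counts as a responder in all seven.

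The size cannot be fixed from the documents: 0 points with equal rates, up to about 10 points under the assumed unequal rates. Those figures assume 68 and 34 evaluable eyes and that each flagged eye otherwise meets the endpoint. A flagged eye whose Month 12 pressure misses the target, or that needs more drops, changes nothing. The primary conclusion is not affected. This is an inexpensive improvement to how secondary results will be read, not a flaw in the main test.

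**What to change.** In SAP 5.4.2, add "No clinical hypotony" to each of the seven combined endpoints, using the flag derived in SAP 5.3.1. State that flagged eyes are non-responders and stay in the denominator. This needs saying because SAP 1.1.3 speaks of excluding such eyes from complete and qualified success, which could be read as dropping them. Record the change in SAP Appendix 2, since Protocol 7.2 and SAP 1.1.3 give these endpoints without the condition, and do so before database lock.

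Leave the plain pressure and percentage cut-offs and the medication-free versions as defined. Beside each, report the number of responding eyes with clinical hypotony and the number at 6 mm Hg or less at Month 12. The adverse-event lists define hypotony as below 6 mm Hg, so the tables should say which threshold they use.

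The cost is one condition in seven derivations plus two count columns. There are two downsides. The flag applies at any time point, so an eye with early clinical hypotony that resolved also becomes a non-responder, as it already does in the primary. The flag also does not catch low pressure without vision loss; the added counts make those eyes visible. The combined endpoints lack the primary's count-fingers and secondary-surgery conditions too, so this change alone does not nest them fully within the primary.
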